1. SYNOPSIS

Study Title: The Intra-arterial Vasospasm Trial - A Multicenter Randomized Study

Objectives: The primary objective of the study is to determine the optimal intra-arterial drug treatment regimen for arterial lumen restoration after cerebral vasospasm following aneurysmal subarachnoid hemorrhage.

The secondary objective is to evaluate clinical outcome 90 days after patient discharge following in-hospital optimal intra-arterial drug treatment for cerebral vasospasm.

Design: This study is a prospective multicenter randomized trial.

Outcome variables: The primary outcome measure is the post-infusion improvement ratio (PIIR) assessed 10 minutes after completion of the intra-arterial infusion. PIIR is a measure of arterial lumen diameter pre- and post-intra-arterial drug infusion in the presenting vasospasmic blood vessel.

Modified Rankin Scale (mRS) at 3 months post-hospital discharge will be recorded as a secondary outcome to assess overall clinical outcome.

Interventions: The interventions in this study are part of the routine standard of care (SOC) procedures for cerebral vasospasm treatment. Following surgical or endovascular intervention for aneurysmal subarachnoid hemorrhage (aSAH) if patients develop cerebral vasospasm refractory to maximal medical management, endovascular treatment by intra-arterial drug infusion of a single drug agent or a cocktail of drug agents will be initiated.

Study participants will be randomly assigned to one of the three treatment groups where one single drug agent or a cocktail of drug agents will be intra-arterially administered. *Group 1* will be treated with nicardipine. *Group 2* will be treated with verapamil and *Group 3* will be treated with the combination of verapamil, nitroglycerin and nicardipine. Pre- and post-infusion vasospasmic vessel diameters will be compared. The change in diameter will be quantified based on the mean percentage change. At three months post-hospital discharge, study participants will be followed up in clinic to evaluate clinical outcomes.

Duration: The total duration for study participation required is the standard hospital stay for postaSAH vasospasm treatment and one follow-up clinic visit at 3 months following hospital discharge.

Sample Size: The study will require a maximum of 330 patients, 110 in each of the three treatment regimens. Subjects will be randomized equally into one of three treatment groups.

Population: The patient population will be hospitalized patients presenting with cerebral vasospasm post-aneurysmal subarachnoid hemorrhage.

Study time frame: The total study time frame is 24 months (18 months for enrollment + 3 months follow up and \pm 3 months to accommodate any scheduling conflict and data gathering).

2. STUDY OBJECTIVES

Primary Objective: The primary objective of the study is to determine the optimal intra-arterial drug treatment regimen for arterial lumen restoration after cerebral vasospasm following aneurysmal subarachnoid hemorrhage.

We hypothesize that a cocktail of drug agents via infusion will likely improve treatment efficacy compared to single agents.

Secondary Objective: The secondary objective is to evaluate clinical outcome 90-days after patient discharge following in-hospital optimal intra-arterial drug treatment for cerebral vasospasm

3. BACKGROUND

Rationale & Supporting Data:

Cerebral vasospasm is a devastating health problem that is a major contributor to poor outcome following subarachnoid hemorrhage (SAH). The estimated case fatality following a SAH is 25-50% with a large proportion of these being secondary to the deleterious consequences of delayed cerebral vasospasm^{1, 2}. Up to 70% of patients who survive the initial SAH develop signs of vasospasm, which, if untreated, can lead to devastating strokes ^{1,3,4}. To this date, the armamentarium available for predicting, preventing, and optimizing outcomes following severe vasospasm remains limited.

The reason for this poor result is, in part, that the complex pathogenesis of vasospasm has not been completely explicated. What is clear though is that between 3 and 21 days after SAH, severe vasoconstriction of the intracranial arteries frequently occurs, leading to delayed ischemia and commonly devastating strokes.

Despite improved microsurgical and endovascular techniques used to treat aneurysms, we have not made significant strides in treating cerebral vasospasm. The traditional therapy acutely using hypertensive hypervolemic hemodilution, which has been adopted in clinical practice, presents considerable cardiopulmonary risks. Endovascular treatments such as angioplasty and intra-arterial drug delivery, particularly of calcium channel blockers, have been considered the quintessential treatment for minimizing potential devastating ischemic stroke resulting from delayed cerebral vasospasm.

Based on the results of a recent national survey conducted by the two PI's of this study through the joint AANS/CNS cerebrovascular section, there is considerable variability in how intra-arterial of cerebral vasospasm is treated. This has led to variable outcomes.

The commonly used intra-arterial drugs for treating vasospasm are used as single agents, among them being verapamil⁵, nicardipine^{6, 7} and nitroglycerin. The clinical result is generally considered unsatisfactory. There has been no literature that conclusively recommends an optimal intra-arterial infusion agent or combination of agents for treating cerebral vasospasm, particularly when balloon angioplasty is not feasible for the involved arteries. The end result of treatment is thus generally unsatisfactory.

A retrospective study⁸ was recently conducted in consecutive patients treated for cerebral vasospasm at The University of Texas Medical School, Memorial Hermann Hospital at the Texas Medical Center, a tertiary treatment center in Houston. Two cohorts were involved. Group 1 (N=47 patients, 116 vessels) was treated between 2008-2011 with a single agent; Group 2 (N=69 patients, 106 vessels) was treated between 2010-2013 with a cocktail of multiple agents (nitroglycerin, verapamil, nicardipine). Patient demographics, age, and modified Rankin score (mRS) at discharge and at 3 months were collected in the cerebrovascular database. Arterial luminal diameters were measured in cerebral angiograms both pre-infusion (PrID) and post-infusion (PoID). The Improvement Ratio (IR) = (PoID - PrID/PrID) x 100 was calculated and statistically compared among groups. This study results showed, Group 2 demonstrated a significantly greater improvement IR 45.8% (SD 36.6) than Group 1 IR 10.9% (SD 12.0), P<0.001. Multiple agent therapy. Comparison of the IR between different single agents within Group 1 (nicardipine and verapamil) demonstrated no difference in vessel diameter change. Patient age had no effect on efficacy in either group.

The conclusion of this study is that treatment of cerebral vasospasm with an IA cocktail of nitroglycerine, verapamil, and nicardipine provides significantly better angiographic improvement of vasospasm than does single agent therapy. (This study has been presented at the International Stroke Conference 2014, in San Diego, CA).

This encouraging result has led us to pursue this proposed prospective evaluation of the efficacy of cocktail drug agent infusion therapy versus the current standard of care single agent therapy that is used by the majority of neuro-interventionists throughout the United States.

The goal of this study is to determine the optimal intra-arterial drug treatment regimen for treating cerebral vasospasm.

Given that each of currently commonly used intra-arterial vasodilators (verapamil, nitroglycerin and nicardipine) has its own mechanisms of action despite some of them belonging to the same drug category ⁹, combining these medications for intra-arterial infusion potentially provides synergistic effects of cerebral vasodilation while minimizing cardiovascular instability induced by high doses of single agent treatment.

Based on single center retrospective data from the PI's center, we hypothesize that infusions of cocktail drug agents will improve treatment efficacy compared to single drug agent infusion.

Hypothesis: Intra-arterial (IA) infusion of cocktail drug agents is more efficacious than single drug agent treatment for cerebral vasospasm therapy.

4. STUDY DESIGN

This is a prospective multicenter randomized controlled clinical trial. Endovascular treatment will be initiated on hospitalized patients who present with cerebral vasospasm within 3-21 days following surgical or endovascular intervention for aneurysmal subarachnoid hemorrhage (aSAH). Endovascular treatment will consist of:

- 1. Diagnostic angiogram to locate the spasmic blood vessel/vessels.
- 2. Pharmacological cerebral angioplasty to treat presenting spasm in one or two the following arterial vessel territories (if all three territories need treatment: the patient is excluded from participation in the study)
 - a. Right Carotid Artery Territory: to treat Vasospasm in R Carotid, R ACA, R MCA & its branches
 - b. Left Carotid Artery Territory: to treat Vasospasm in L Carotid, L ACA, L MCA & its branches
 - c. Vertebral-Basilar Territory
- 3. Post-treatment angiogram.
- 4. Balloon angioplasty may be done if vasodilators fail to produce response or show insufficient improvement.

Please refer to Appendix IV Study flow chart for the detailed study design & Flow

Randomization:

Study participants will be randomly assigned to one of three treatment groups. Randomization will be pre-determined and specific to each participating center. At each center only the Research Coordinator/Nurse will have access to the randomization pattern.

Treating physicians will not be blinded by the randomization scheme and will know the drug group assigned to the study subject *only after the first diagnostic angiogram has been performed, when he/she confirms the need for drug treatment.*

However, the subjects enrolled in the trial will be blinded and will not know the treatment group to which they have been assigned.

TREATMENT CRITERIA

- 1. Symptomatic vasospasm clinical symptoms, with or without Trans-cranial Doppler (TCD) study.
- 2. 50% or more stenosis seen on diagnostic angiogram in asymptomatic patients

DRUG DOSE: Patients who qualify for endovascular treatment post aSAH will be randomly assigned to one of three treatment groups:

Group 1: Nicardipine (Cardene): 5 mg per circulation in 25 mL 5% Dextrose. Infusion rate: 1.25 mL/minute over a period of 20 minutes

Group 2: Verapamil: 10 mg per circulation in 10 ml saline. Infusion rate: 1 mL/minute over a period of 10 minutes.

Group 3:

Verapamil 10 mg in 10 mL saline, Infusion rate: 1 mL/minute over a period of 10 minutes + Nitroglycerin (200 mcg in 4 mL 5% dextrose, Infusion rate: 0.5 mL/min over 8 minutes + Nicardipine 5 mg in 25 mL 5% Dextrose, Infusion rate 1.25 mL/min over 20 minutes per circulation (USE DIFFERENT SYRINGES FOR EACH DRUG. DO NOT MIX DRUGS IN THE SAME SYRINGE.)

Perform post-treatment angiogram run minimally 10 minutes after completion of infusion. Angiographic Imaging should be recorded 10 minutes after infusion.

ONLY ONE TREATMENT SESSION is permitted per day.

Drug Dosage: Maximum intra-arterial dose allowed within 24-hour period is, nicardipine 10 mg, verapamil 20 mg, cocktail (verapamil 20 mg, nitroglycerin 400 mcg & nicardipine 10 mg)

Please refer to Appendix V & VI for detailed drug dosage tabulations.

If the study subject needs another treatment after the first treatment session, use the same drug for each repeat treatment.

Additional doses can be given per the treating physician's discretion up to the maximum allowed dose as per the protocol; please record the additional doses and treatment given in the data collection forms.

Balloon angioplasty can be performed if drug infusions show insufficient improvement per the treating physician's discretion.

A central core laboratory will perform radiographic data assessment and assessors will be blinded to treatment group assignment.

The diameters of the same spasm vessel(s) will be compared before (pre-) and after (post-) infusion of the agent/agents, (see figure below).

The diameters will be measured at the following locations: ICA supraclinoid segment, MCA M1, MCA M2, ACA A1, ACA A2 & Basilar

The pre-treatment diameter measurement will be at the narrowest spot as is shown in the figure below. The post-treatment diameter measurement will be at the same location as the one prior to the infusion treatment.

Pre-infusion

Post-infusion

The changes will be quantitated based on the ratio percentage as shown in the following formula.

Post-infusion improvement ratio (PIIR) = (B - A)/A

Example: A = 1 mmB = 1.2 mm

PIIR % = (1.2 - 1)/1 = 20%

If balloon angioplasty is performed, the artery diameter will still be measured and the measurement documented.

Clinical data, that will be collected and entered in REDCap are as follows:

- Patient demographics (age, gender, BMI, race)
- Patient medical and surgical history
- Patient's current medications
- The length of time from aneurysm rupture to time of surgical intervention
- Time in between vasodilator applications
- Number of drug applications used
- Dose of drug applications
- Pre- and post-procedure intracranial pressure measurements (ICPs)
- Cardiovascular instability (SBP changes in mm Hg, requirement of intravenous [IV] pressors)
- New strokes on CT
- Modified Rankin Scale, NIHSS (before treatment, at discharge, and at 3 months after discharge)

Patients will have a 3-month follow-up clinic visit as per standard of care after discharge from the hospital.

5. SELECTION AND ENROLLMENT OF SUBJECTS

Inclusion Criteria: Only adult patients ≥ 18 years with ruptured aneurysms requiring surgery or endovascular therapy and who experience vasospasm post-operatively (3-21 days post-procedure) will be enrolled in this study.

Informed consent will be obtained either from the patient or the patient's legal representative. The institutional PI/Co-PI will determine the **eligibility of the patients** for the study on the basis of the following:

- Adult patient, age 18 80 years old, with ruptured aneurysm(s) who experience vasospasm postoperatively within 3-21 days.
- Symptomatic vasospasm (clinical or TCD)
- For centers that perform a routine day 7 angiogram post-aneurysm treatment 50% or more stenosis seen on diagnostic angiogram for asymptomatic patients.

Exclusion Criteria:

- Inability to obtain consent from patient or patient's family
- Pregnant women (confirmed by a positive pregnancy test)
- Hunt Hess (HH) grade 5
- Intra-arterial drug treatment in all 3 arterial territories

Study Centers:

The University of Texas Medical School at Houston University of Illinois College of Medicine – Chicago Geisinger Health System, North Shore University Hospital – Northwell Health

Study Enrollment Procedures:

Institutional PI & Co-PI will determine a patient's eligibility based on SOC testing and procedures used in treating patients with aneurysms.

For patients who develop vasospasm during their hospital stay due to aSAH, the PI and members of his research team will approach them to request participation in the clinical study. The study procedures will be explained to the patient or his/her legal representative in detail and consent forms for the study will be explained in detail. Any questions or concerns the participants have will be answered in detail, before the patient or his/her representative signs the consent forms and the potential participants will be given ample time to make an informed decision. For women who have to be excluded from participating in the study on the basis of a suspected pregnancy, a pregnancy test needs to be performed to confirm the pregnancy.

The study coordinator at each site will maintain a log sheets of all the enrolled participants and potential participants approached for the study, eligible participants who refuse to participate & reasons for nonparticipation.

The University of Texas Medical School at Houston is the primary center and will maintain records from all other participating centers.

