- Off-Study Requirements: Study participants will be followed up in clinic at 3 months post-discharge from hospital. All participants will receive this follow-up visit, even if the study intervention was discontinued.

Informed Consent: Informed consent process will take place in a private room where the PI/Co-PI and or the study coordinator will explain the study trial and enrollment process to the potential participants. They will be given ample time to understand the study and to be asked if they have any questions or concerns.

The Informed Consent form is attached in the appendix below.

Documentation of vasospasm: By clinical symptoms, transcranial doppler ultrasound, CT-angiogram & cerebral angiogram.

Clinical Assessments: A complete neurological examination will be done & Modified Rankin score (mRS), NIHSS will be noted. At 3-month follow-up appointment, there will be a recording taken during the mRS evaluation. This recording will contain only the Subject ID and the mRS questions and answers.

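### Site coordinators or nurses have access to the pre-determined, centre-specific randomisation pattern, and the readable text neither conceals upcoming assignments from them nor keeps them out of approach and consent

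*Combined protocol and SAP*

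**What the plan says.** On the sequence and who can reach it, Section 4 (Randomization) says: "Randomization will be pre-determined and specific to each participating center", and then "At each center only the Research Coordinator/Nurse will have access to the randomization pattern".

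On who recruits, Section 5 (Study Enrollment Procedures) says that "the PI and members of his research team will approach them to request participation in the clinical study". Section 7 (Informed Consent) says: "Informed consent process will take place in a private room where the PI/Co-PI and or the study coordinator will explain the study trial". Section 6 (Handling of Study Interventions) has the site study coordinator keep the log of randomisation, enrolment and withdrawal. Section 5 has the same role keep the log of people approached.

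The plan also contains safeguards:
- Eligibility (Section 5): "Institutional PI & Co-PI will determine a patient's eligibility based on SOC testing and procedures".
- Treating physician (Section 4): learns the arm "only after the first diagnostic angiogram has been performed, when he/she confirms the need for drug treatment".
- Subjects (Section 4): blinded to their arm.
- Outcome reading (Section 4): "A central core laboratory will perform radiographic data assessment and assessors will be blinded to treatment group assignment".
- Screening record (Section 5): the coordinator's log includes "eligible participants who refuse to participate & reasons for nonparticipation".
- Monitoring (Section 10, Data and Safety Monitoring): centres are monitored yearly, or after each further two completed subjects if that comes sooner.

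**The concern.** Randomisation protects the comparison only if the people who influence entry cannot know the next arm. Someone who knows it, and who also decides whom to approach or how to present the trial, can let entry depend on the arm without intending to. The protocol states a directional hypothesis in favour of the cocktail (Sections 2 and 3), so unconscious steering needs no bad faith.

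What is at stake is whether the three arms are comparable at entry. Blinded core-laboratory reading protects the measurement of PIIR; it does nothing about who was enrolled into which arm. The interim and final comparisons in Section 10 are ANOVAs of PIIR by arm with no baseline covariates named, and the baseline-adjusted models are labelled exploratory. An imbalance produced at entry would therefore pass unadjusted into the final test and into the interim decisions to drop an arm.

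**Working it through.** No formula applies. The point concerns access and roles, not sample size, power or error rate, and the plan gives no figure to reproduce. The check is to set the relevant provisions side by side.

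1. **Is the sequence knowable in advance?** Section 4 makes it pre-determined and one per centre. Section 10 gives a 1:1:1 ratio. No block structure is described.

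2. **Who can reach it?** At the site, only the Research Coordinator/Nurse. The word for what they reach is the pattern. The plain reading is sight of upcoming assignments, but access to each assignment as it falls due is not excluded by the wording. The difference matters. Under simple 1:1:1 randomisation (an assumption), a person without the list guesses the next arm correctly about 1 time in 3; a person who can read the list knows it.

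3. **Can that person influence entry?** Section 5 lets any member of the research team approach candidates and excludes no one. Section 7 names the study coordinator among those who may explain the trial. The titles differ: Section 4 says Research Coordinator/Nurse, while Sections 5, 6 and 7 say study coordinator. Section 6 gives the study coordinator the randomisation log, which makes overlap likely but does not state it.

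4. **Does any provision conceal the sequence from the list-holder or keep that person out of recruitment?** The readable text describes no central or web-based release, no sealed assignments, no pharmacy-held list, and no rule barring the list-holder from approach or consent. Section 11 describes REDCap for data entry only. The flow chart in Appendix IV is not shown in the copy reviewed.

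5. **What does each safeguard cover?**
- PI/Co-PI eligibility decisions limit who qualifies, not who is approached or how the trial is explained.
- Delayed disclosure covers the treating physician, not the list-holder.
- Subject blinding means that a refusal should not reflect the patient's own knowledge of the arm; it does not govern how the trial was presented.
- The blinded core laboratory covers measurement.
- The log of approaches and refusals, and site monitoring, may help to detect selective entry afterwards. They do not prevent it, and the log is kept by the study coordinator.

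6. **What remains?** Influence at approach and explanation by a person who may know the next arm.

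7. **Can it be sized?** No. The documents give no rate of selective approach or refusal. The only patient factor that they relate to vessel response is age, reported in Section 3 to have had no effect in the retrospective study.

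**The case against.** The best defence is that the exposure is narrow. Access at the site is limited to one role. Eligibility belongs to the PI/Co-PI. Consent comes before assignment, which takes place in the interventional suite (Section 6), and the treating physician confirms the need for drug treatment before learning the arm. Subjects are blinded. Access to the pattern may mean no more than retrieving each assignment when it is due, the list-holder may never recruit, and the missing flow chart may settle the matter. The unadjusted ANOVA does not create a concealment problem, and covariate adjustment would not reliably cure selection on unmeasured factors.

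Most of this stands as a limit on the point. Eligibility decisions and the physician's confirmation are shielded on paper, and the absence of covariates is a consequence to note, not the fault. What does not stand is the conclusion that nothing needs changing. The protocol positively grants access to a pre-determined sequence and nowhere sets a barrier between that access and recruitment.

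A reader might infer that the recruiting coordinator openly holds the list. The documents do not support that: they never identify the two roles as one person, and they do not say what form the access takes.

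**Conclusion.** The point holds as a weakness in allocation concealment and should be fixed. Confidence is high that the readable text neither separates the list-holder from recruitment nor conceals upcoming assignments from that person. Confidence in the harm pathway is moderate, because it rests on three assumptions: that access to the pattern means sight of upcoming arms, that the list-holder takes part in approach or explanation, and that the flow chart contains no contrary provision.

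No size of bias can be given. A reader might go further and infer that entry was selective, or that the PIIR comparison is biased. Nothing in the documents shows either; the design leaves the possibility open and no more. Nor does the point reach the PI/Co-PI's eligibility decisions, the physician's decision to treat, or the core laboratory's measurements, each of which has its own stated safeguard.

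**What to change.** Replace the sentence in Section 4 that grants the Research Coordinator/Nurse access to the pattern. State instead that the centre-specific sequences are held centrally, out of view of all site staff. Each assignment should be released singly, after consent and after the treating physician has confirmed the need for drug treatment on the diagnostic angiogram. That is the moment at which Section 4 already discloses the arm to the physician, so the timing of that disclosure does not change.

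If central release cannot be obtained, the minimum is one added sentence: whoever holds the list takes no part in approaching, informing or consenting candidates. If either arrangement is already in use, the protocol should say so.

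This is a cheap improvement and needs no extra patients. The costs are the set-up of a central release service, since Section 11 does not establish that REDCap will randomise, and the protocol wording. There may also be some waiting for drug preparation after the angiogram. The documents do not say when the drug is prepared, so this delay cannot be ruled out, and Appendix III (Monitoring Plan) places patients under general anaesthesia during the infusion treatment. Sites should confirm their preparation times before the change is adopted.
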